9.7.1.7.2 PHARMACODYNAMIC, PHARMACOGENOMIC, AND OTHER BIOMARKER ANALYSES

Pharmacodynamic, PGx, and other biomarker analyses may be performed and reported separately. Details of these analyses may be described in a separate statistical analysis plan. Please also refer to [Appendix 3](#).

Pharmacodynamic Analyses

The PD Analysis Set will be used for the summaries and analyses of PD biomarkers (CSF and plasma biomarkers, MRI endpoints). The percentage change from baseline in CSF A β (1-x), A β (1-42), A β (1-40), t-tau, p-tau, and BACE1 variables (eg, activity and protein levels) from 4 weeks and up to 18 months of treatment will be analyzed and presented graphically. (revised per Amendment 05) Baseline levels and changes in t-tau and p-tau will be correlated with changes in CSF A β (1-42), imaging markers, and *ApoE4* status. (revised per Amendment 04)

Summary statistics for CSF biomarkers will be assessed for evidence of a dose relationship.

Pharmacokinetic and Pharmacodynamic Analyses

The PK/PD relationship between CSF biomarker levels, amyloid load on PET, vMRI, and elenbecestat (E2609) dose, plasma, and CSF exposure will be initially explored graphically and any emergent relationship will be explored through population PK/PD modeling. The PK/PD relationship between plasma PK parameters with other biomarkers may also be explored using similar methods. (revised per Amendment 04)

The relationship between plasma and CSF exposure to elenbecestat (E2609) and the clinical efficacy scales (eg, MMSE, CDR) will be explored graphically. Additionally, the relationship between plasma exposures of elenbecestat (E2609) and select lymphocyte parameters will be explored graphically, and any emergent relationship will be explored using population-based modeling methods. (revised per Amendment 04)

Exposure-safety analyses may also be conducted.

Pharmacogenomic Analyses

Blood samples will be used to determine the *ApoE* genotype and the *NAT2* phenotype of subjects enrolled in this study. The genomic DNA samples may also be stored and used as described in [Section 9.7.1.7.2](#). Details of PGx testing may be provided and reported separately.

9.7.1.8 Safety Analyses

Evaluations of safety will be performed on the Safety Analysis Set. The incidence of AEs (including changes from baseline in physical and neurological examinations, and dermatological assessments), out-of-normal-range laboratory safety test variables, abnormal ECG findings, out-of-range vital signs, suicidality (C-SSRS), and results of the sleep questionnaire, along with the change from baseline in laboratory safety test variables, ECGs, safety MRI, vital sign measurements, and cognitive decline assessment such as CBB will be summarized by treatment group using descriptive statistics. (revised per Amendment 05)

9.7.1.8.1 EXTENT OF EXPOSURE

The extent of exposure to study drug will be summarized as cumulative extent of exposure in 3-month intervals. The cumulative number and percent of subjects will be presented by treatment group. Duration of exposure will be summarized using descriptive statistics as continuous variable as well as categorical variable in 3-month intervals and the number and percent of subjects will be presented by treatment group.

9.7.1.8.2 ADVERSE EVENTS

The AE verbatim descriptions (investigator terms from the eCRF) will be classified into standardized medical terminology using the Medical Dictionary for Regulatory Activities (MedDRA). Adverse events will be coded to the MedDRA (Version 17.0 or higher) lower level term closest to the verbatim term. The linked MedDRA preferred term and primary system organ class (SOC) are also captured in the database.

A TEAE is defined as an AE that emerges during treatment, having been absent at pretreatment (Baseline) or

- Reemerges during treatment, having been present at pretreatment (Baseline) but stopped before treatment, or
- Worsens in severity during treatment relative to the pretreatment state, when the AE is continuous.

Only those AEs that are treatment-emergent will be included in summary tables. All AEs, treatment-emergent or otherwise, will be presented in subject data listings.

The TEAEs will be summarized by treatment group on the Safety Analysis Set. The incidence of TEAEs will be reported as the number (percentage) of subjects with TEAEs by SOC and preferred term. A subject will be counted only once within an SOC and preferred term, even if the subject experienced more than 1 TEAE within a specific SOC and preferred term. The number (percentage) of subjects with TEAEs will also be summarized by maximum severity (mild, moderate, or severe). The number (percentage) of subjects with TEAEs will also be summarized by relationship to study drug (Yes [related] and No [not related]).

The number (percentage) of subjects with treatment-related TEAEs will be summarized by SOC and preferred term. Treatment-related TEAEs include those events considered by the investigator to be related to study drug. The number (percentage) of subjects with treatment-related TEAEs will also be summarized by maximum severity (mild, moderate, or severe).

Adverse events will be summarized by the following subgroups: *ApoE4* status (positive or negative), prior treatment with AChEIs or memantine (no or yes), and clinical population (MCI/Prodromal or mild to moderate AD). (revised per Amendment 01)

The number (percentage) of subjects with TEAEs leading to death will be summarized by MedDRA SOC and preferred term for each treatment group. A subject data listing of all AEs leading to death will be provided.

The number (percentage) of subjects with treatment-emergent SAEs will be summarized by MedDRA SOC and preferred term for each treatment group. A subject data listing of all SAEs will be provided.

The number (percentage) of subjects with TEAEs leading to discontinuation from study drug will be summarized by MedDRA SOC and preferred term for each treatment group. A subject data listing of all AEs leading to discontinuation from study drug will be provided.

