In the MAD study, AEs of interest included relapse of orolabial herpes, viral respiratory tract infection, drug rash, and abnormal dreams. More details are available in the Investigator's Brochure. In summary, elenbecestat (E2609) administered at doses of 200 and 400 mg was associated with reductions in CD4 (T helper cells), CD8 (cytotoxic T cells), and CD19 (B cells) counts at Day 8. These reductions were more clearly evident by Day 15, consistent with a treatment by time interaction in the statistical analysis. There was evidence that the lower doses of 50 to 100 mg also caused some reduction in CD4 lymphocyte counts by Day 15. Doses above 100 mg appeared to be associated with greater reductions in CD4 and CD8 lymphocyte counts, which occurred earlier in the treatment period compared with the effects of 25 to 100 mg doses. These effects on lymphocyte counts gradually resolved from Day 20 to Day 35, which were 6 and 21 days, respectively, after administration of the last dose of elenbecestat (E2609) on Day 14. Reductions in CD4 and CD8 lymphocyte counts at doses of 200 and 400 mg to a level close to or less than the lower limit of normal (LLN) could be associated with increased risk of developing relapse of orolabial herpes or other infections.

In Study 003, a drug-drug interaction study, PK results showed that itraconazole (a potent inhibitor of cytochrome P450 [CYP3A4] and carboxyesterase-2 [CES2]) increased by approximately 70% the area under the concentration \times time curve (AUC) of elenbecestat (E2609). Consequently, strong inhibitors of CYP3A4 will be prohibited in this study.

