8.1 Primary Objective

(revised per Amendment 05)

The primary objective is:

- To assess the safety (including immunological and hematological parameters) and tolerability of daily dosing with elenbecestat (E2609) in MCI/Prodromal subjects and in subjects with mild to moderate AD (revised per Amendment 01)

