9.5.1.5.1 ADVERSE EVENTS AND EVENTS ASSOCIATED WITH SPECIAL SITUATIONS

An AE is any untoward medical occurrence in a subject or clinical investigation subject administered an investigational product. An AE does not necessarily have a causal relationship with the medicinal product. For this study, the study drug is elenbecestat (E2609).

The criteria for identifying AEs in this study are:

- Any unfavorable and unintended sign (including an abnormal laboratory finding), symptom, or disease temporally associated with the use of an investigational product, whether or not considered related to the investigational product (Note: It is not necessary to report every sign or symptom as a separate AE if the overall disease [diagnosis] is being reported as an AE.)
- Any new disease or exacerbation of an existing disease
- Any deterioration in nonprotocol-required measurements of a laboratory value or other clinical test (eg, ECG or x-ray) that results in symptoms, a change in treatment, or discontinuation of study drug
- Recurrence of an intermittent medical condition (eg, headache) not present pretreatment (Baseline)
- An abnormal laboratory test result should be considered an AE if the identified laboratory abnormality leads to any type of intervention, discontinuation of study drug, or withholding of study drug, whether prescribed in the protocol or not

All AEs observed during the study will be reported on the eCRF. All AEs, regardless of relationship to study drug or procedure, should be collected beginning from the time the subject signs the study ICF through the last visit during the Core Study (Visit 20, as shown in [Table 7](#), for subjects who do not enter the OLE Phase) or the last Visit during the OLE Phase (Visit 34 as shown in [Table 14](#), for subjects who participate in the OLE Phase). (revised per Amendment 07) Subjects who fail screening primarily due to AE(s) must have the AE(s) leading to screen failure reported on the Screening Disposition eCRF. SAEs will be collected for 3 months after the last dose of study drug, (ie, through to the final Follow-Up visit [Visit 20 for subjects who do not enter the OLE Phase or Visit 34 for subjects who participate in the OLE Phase]). (revised per Amendments 04, 05, and 07)

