9.7.1.1 Study Endpoints

9.7.1.1.1 PRIMARY ENDPOINT

- Safety and tolerability, which include incidence of TEAEs and SAEs, laboratory parameters, vital signs, and ECG parameters (revised per Amendment 05)

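### Adverse events and SAEs that start after the last dose are collected for 12 weeks but, as the TEAE rule is written, get no by-arm table

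*Protocol*

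**What the plan says.** Section 9.7.1.8.2 gives the definition: "A TEAE is defined as an AE that emerges during treatment, having been absent at pretreatment (Baseline) or", followed by two further limbs for events that come back or get worse. All three limbs are tied to treatment, and none carries a number of days after the last dose.

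The same section then fixes what is tabulated: "Only those AEs that are treatment-emergent will be included in summary tables". For everything else, "All AEs, treatment-emergent or otherwise, will be presented in subject data listings". SAEs follow the same rule: "The number (percentage) of subjects with treatment-emergent SAEs will be summarized by MedDRA SOC and preferred term for each treatment group". The death table counts TEAEs leading to death.

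Three other places bear on this:

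- Section 9.7.1.1.1 (primary endpoint): "Safety and tolerability, which include incidence of TEAEs and SAEs, laboratory parameters, vital signs, and ECG parameters". SAEs carry no treatment-emergent limit here.
- Section 9.5.1.5.1 (collection): AEs run to Visit 20 in the Core Study, or Visit 34 for subjects in the open-label extension (OLE), and "SAEs will be collected for 3 months after the last dose of study drug".
- Section 7.2 (multiple-dose study): "These effects on lymphocyte counts gradually resolved from Day 20 to Day 35, which were 6 and 21 days, respectively" after the last dose.

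**The concern.** Safety is the primary endpoint, and Section 8.1 names immunological parameters as part of it. The protocol expects the drug's effect on lymphocytes to outlast dosing: Table 7 schedules blood counts and lymphocyte subsets at all four post-dose visits (weeks 2, 4, 8 and 12) and immunoglobulins at weeks 4, 8 and 12. If counts can still be low after the last dose, an infection or herpes relapse starting then is one of the events the follow-up is meant to catch. The tabulation rule leaves that event out of every by-arm incidence table. The SAE tables would also report something narrower than the primary endpoint.

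**Working it through.** The protocol states no figure that depends on the TEAE definition, so there is none to reproduce. The check is textual, with some arithmetic on time.

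**1. Can treatment be read to include follow-up?** Three places say no. Section 9.1.2 splits the Randomization Phase into a 78-week Treatment Period and a 12-week Follow-up Period after the last dose. Section 9.2.5 describes the week 2, 4, 8 and 12 visits as off-treatment. Section 9.7.1.5 closes the definition of concomitant medication at the last dose and mentions follow-up medication separately.

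**2. Follow events through the rules.**

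| Event | Collected (9.5.1.5.1) | TEAE (9.7.1.8.2) | By-arm AE table | Listing |
|---|---|---|---|---|
| Starts on drug, first recorded after last dose | yes | yes | yes | yes |
| Starts after last dose, not serious | yes | no | no | yes |
| Starts after last dose, serious or fatal | yes | no | no | yes |

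The last row is where Sections 9.7.1.1.1 and 9.7.1.8.2 disagree: the SAE belongs to the primary endpoint but is not in the SAE table.

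**3. What is not affected.** Section 9.7.1.8.3 summarizes laboratory values, including lymphocyte subsets and immunoglobulins, at each postbaseline visit, and defines markedly abnormal values on any postbaseline result. Post-dose laboratory findings therefore reach the tables. Only clinical events are affected.

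**4. Time outside the AE tables.** Share = follow-up weeks / (treatment weeks + follow-up weeks), with 12 weeks of follow-up:

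- completer: 12 / (78 + 12) = 12/90 = 13.3%
- stops at week 52: 12/64 = 18.8%
- stops at week 26: 12/38 = 31.6%
- stops at week 12: 12/24 = 50%

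A 28-day window would recover 4 of those 12 weeks. On a base of treatment plus 4 weeks, that is 4/82 = 4.9% for a completer and 4/16 = 25% for a week-12 stop. The other 8 weeks would fall to a separate table.

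**5. Recovery interval.** The last dose in the multiple-dose study was on Day 14. Resolution ran from Day 20 to Day 35, that is 20 − 14 = 6 to 35 − 14 = 21 days after it. This lies wholly inside the untabulated period, and within a 28-day window.

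**6. Weight of one event.** At about 15 subjects per arm (Section 9.7.2), one subject is 1/15 = 6.7 percentage points of an arm.

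**The case against.** The strongest reply is that this belongs to the SAP: a protocol often states the general TEAE idea and leaves the lag in days to the SAP, which Section 9.7.1 says will be finalized before database lock. That would answer a charge of silence. Here the protocol does more than stay silent: it fixes a rule, restricts the tables to events meeting it, and contradicts its own primary endpoint on SAEs. The SAP may well add a window, but it would be departing from the protocol text.

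A second reply is that nothing is hidden. All AEs, all SAEs and all AEs leading to death are listed, the safety analysis is descriptive, and with about 15 subjects per arm listings can be read case by case. This stands and lowers the severity, but a listing does not give incidence by arm.

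Third, the biological case is modest. In the multiple-dose study the clearest reductions were at 200 and 400 mg. Section 9.4.4 reports no infections at 100 mg or below and puts exposure at this trial's 50 mg below that of the 100 mg capsule. Section 7.2 does report some CD4 reduction at 50 to 100 mg. The case supports looking at the period; it does not predict events there.

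A reader might also infer more than the documents support:

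- *That an infection first found at the Early Discontinuation Visit is lost.* The definition turns on onset or worsening, so it is lost only if it began after the last dose.
- *That post-dose immune monitoring drops out of the tables.* It does not (step 3).
- *That the omission favors the active drug.* This would need more early stopping or more post-dose events on active drug, and no document figure shows either.

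**Conclusion.** The point holds for clinical events with onset after the last dose. As written, such AEs, SAEs and deaths are collected and listed but have no by-arm incidence, and the SAE tables are narrower than the SAE component of the primary endpoint. The period concerned is 13.3% of post-first-dose time for a completer, rising to 50% for a subject who stops at week 12. These shares should not be read as proportions of events missed; the documents give no event rates from which to estimate that. The direction of any bias is unknown.

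The conclusion assumes that *during treatment* has the meaning that the protocol's own period definitions give it, and that no SAP text overrides it. Because the data are collected and listed and the remedy is small, this is a should-fix.

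**What to change.** In Section 9.7.1.8.2, define treatment-emergent as onset, re-emergence or worsening from the first dose to a stated number of days after the last dose. The window should cover at least the 21-day lymphocyte recovery. Twenty-eight days would do so; Section 9.5.4.2 already uses 28 days for pregnancy reporting, though that alone does not establish it as the right AE window.

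Apply the window to the SAE and death tables. Add one by-arm table of AEs, SAEs and deaths with later onset up to Visit 20 (Visit 34 in the OLE, since Appendix 6 says its safety analysis follows the Core Study). The two sets of tables together would then match the primary endpoint's SAE component. Carry the same wording into the SAP before database lock.

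The cost is a changed definition and one extra table. No visit, sample or form changes. The downside is that a few unrelated post-dose events will be counted in every arm, including placebo.

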9.7.1.8.3 LABORATORY VALUES

Laboratory results will be summarized using International System of Units, as appropriate. For all quantitative parameters listed in [Section 9.5.1.5.3](#), the actual value and the change from baseline to each postbaseline visit and to the end of treatment (defined as the last on-treatment value) will be summarized by visit and treatment group using descriptive statistics. Qualitative parameters listed in [Section 9.5.1.5.3](#) will be summarized using frequencies (number and percentage of subjects), and changes from baseline to each postbaseline visit and to end of treatment will be reported using shift tables. Percentages will be based on the number of subjects with both nonmissing baseline and relevant postbaseline results.

Laboratory test results will be assigned a low/normal/high (LNH) classification according to whether the value was below (L), within (N), or above (H) the laboratory parameter's reference range. Within-treatment comparisons for each laboratory parameter will be based on 3-by-3 tables (shift tables) that compare the baseline LNH classification to the LNH classification at each postbaseline visit and at the end of treatment. Similar shift tables will also compare the baseline LNH classification to the LNH classification for the highest and lowest value during the treatment period.

[Appendix 1](#) (Sponsor's Grading for Laboratory Values) presents the criteria that will be used to identify subjects with treatment-emergent markedly abnormal laboratory values (TEMAVs). Except for phosphate, a TEMAV is defined as a postbaseline value with an increase from baseline to a Grade of 2 or higher. For phosphate, a TEMAV was defined as a postbaseline value with an increase from baseline to a Grade of 3 or higher. When displaying the incidence of TEMAVs, each subject may be counted once in the laboratory parameter high and in the laboratory parameter low categories, as applicable.

Lymphocyte subsets measured (including but not limited to CD4 [T helper cells], CD8 [cytotoxic T cells], CD19 [B cells], CD16/CD56 [natural killer cells] and CD14 [macrophages] and regulatory T cells) will be summarized in the same manner as other laboratory parameters. Mean lymphocyte subsets and the mean change from baseline in lymphocyte subsets will also be displayed graphically over time by dose.

Serum IgG, IgM, and IgA will be measured and summarized in the same manner as other laboratory parameters.

9.7.1.8.4 VITAL SIGNS

Descriptive statistics for vital signs parameters (ie, systolic and diastolic BP, pulse, respiratory rate, temperature, weight), and changes from baseline will be presented by visit and treatment group.

9.7.1.8.5 ELECTROCARDIOGRAMS

Descriptive statistics for ECG parameters and changes from baseline will be presented by visit and treatment group. Shift tables will present changes from baseline in ECG interpretation (categorized as normal; abnormal, not clinically significant; and abnormal, clinically significant) to the end of treatment.

In addition, the number (percentage) of subjects with at least 1 postbaseline abnormal ECG result in QTcF during the treatment period will be summarized. Clinically abnormal ECG results in QTcF will be categorized as follows:

Absolute QTc interval prolongation:

- QTc interval >450 msec
- QTc interval >480 msec
- QTc interval >500 msec

Change from baseline in QTc interval:

- QTc interval increases from baseline >30 msec
- QTc interval increases from baseline >60 msec

9.7.1.8.6 OTHER SAFETY ANALYSES

Cognitive decline will be assessed as a safety assessment, in addition to efficacy assessments. Cognitive assessments will include CBB ([Section 9.7.1.6](#)). (revised per Amendment 05)

9.7.2 Determination of Sample Size

A total of 15 subjects per dose group is deemed sufficient to derive adequate safety and PK/PD data to aid in the selection of appropriate doses and the design of the Phase 3 studies that may be planned subsequently. (revised per Amendment 05)

9.7.3 Interim Analysis

In order to make decisions about the remainder of the study as well as the full elenbecestat (E2609) clinical development program, the sponsor will unblind safety, PK, and PD data on an ongoing basis and perform interim analyses of these data. Investigators, other clinical site staff, subjects, caregivers/informants, and study team will remain blinded to study treatment. (revised per Amendments 03 and 05)

An interim safety analysis will also be conducted when all subjects have completed 12 weeks of treatment (or discontinue study drug early). (revised per Amendments 01, 03, 04, and 05)

9.7.4 Other Statistical/Analytical Issues

Stratification (revised per Amendment 01)

Within the 2 clinical cohorts (MCI/Prodromal and mild to moderate AD), subjects will be stratified at randomization by *ApoE4* status (positive or negative) and prior treatment with AChEIs or memantine or both (yes or no). (revised per Amendment 01)

9.7.5 Procedure for Revising the Statistical Analysis Plan

If the statistical analysis plan needs to be revised after the study starts, the sponsor will determine how the revision impacts the study and how the revision should be implemented. The details of the revision will be documented and described in the clinical study report.

11 PROCEDURES AND INSTRUCTIONS (ADMINISTRATIVE PROCEDURES)

11.1 Changes to the Protocol

Any change to the protocol requires a written protocol amendment or administrative change that must be approved by the sponsor before implementation. Amendments specifically affecting the safety of subjects, the scope of the investigation, or the scientific quality of the study require submission to health or regulatory authorities as well as additional approval by the applicable IRBs/IECs. These requirements should in no way prevent any immediate action from being taken by the investigator, or by the sponsor, in the interest of preserving the safety of all subjects included in the study. If the investigator determines that an immediate change to or deviation from the protocol is necessary for safety reasons to eliminate an immediate hazard to the subjects, the sponsor's medical monitor and the IRB/IEC for the site must be notified immediately. The sponsor must notify the health or regulatory authority as required per local regulations.

Protocol amendments that affect only administrative aspects of the study may not require submission to health or regulatory authority or the IRB/IEC, but the health or regulatory authority and IRB/IEC (or if regionally required the head of the medical institution) should be kept informed of such changes as required by local regulations. In these cases, the sponsor may be required to send a letter to the IRB/IEC and the Competent Authorities (or, if regionally required, the head of the medical institution) detailing such changes.

